1.1 Study design

1.1.1 Study Design

This study is a 2-treatment period, randomized, multicenter parallel-group safety study ([Figure 1-1](#)). Treatment Period 1 is a 52-week, double-blind treatment period in which QAW039 or placebo is added to Global Initiative of Asthma (GINA) steps 3, 4 and 5 standard-of-care (SoC) asthma therapy. Treatment Period 2 is an optional 104-week, single-blind treatment period in which patients will receive QAW039 or placebo added to GINA steps 3, 4 and 5 SoC asthma therapy.

[figure not shown]
Note: For the purpose of this study, single-blind means investigators and patients will remain blinded while all Novartis personnel will be unblinded.

Two categories of patients will be enrolled:

- **Rollover patients:** patients completing a prior Phase 3 study (A2307, A2314, A2316, or A2317) of QAW039 on active study treatment (i.e., did not discontinue blinded study treatment prematurely); and
- New patients:** patients with inadequately controlled asthma who had not previously participated in a study of QAW039.

Patients who successfully complete the treatment period of a prior Phase 3 study of QAW039 will be permitted to enter Study A2315 directly upon the completion of the treatment period of the prior study without completing an off drug follow-up period in the prior study. For these patients completing a prior Phase 3 study of QAW039, the last visit of the treatment period in the prior study and Visit 1 of Study 2315 will occur on the same day (i.e., on the last day of study drug treatment in the prior study). Additionally, for patients completing a prior Phase 3 study of QAW039, Visit 201 of Study 2315 will occur the following day (1 day after completion of the last visit of the treatment period of the prior study and Visit 1 of this study [Study A2315]) so that there is no interruption in study drug treatment.

Figure 1-1 Study design

1.1.2 Randomization scheme

Overall, there is an **approximately 85% chance patients will receive QAW039 in Study A2315**. For patients who participated in a prior Phase 3 study, there is **at least 57% chance a patient will remain on the same QAW039 dose they received in the prior study in Study A2315**.

[Table 1-1](#) shows the randomized allocation of patients into treatment groups in Study A2315.

Table 1-1 Randomized Allocation of Patients into Treatment groups

Patients completing A PRIOR PHASE 3 STUDY OF QAW039: treatment allocation in Study A2315			
Prior study	Treatment group in prior study	Randomization ratio in Study A2315	Treatment group in Study A2315
CQAW039A2307 CQAW039A2314	450 mg once daily	5	QAW039 450 mg once daily QAW039 150 mg once daily Placebo
		1	
		1	
CQAW039A2316 CQAW039A2317	150 mg once daily	1	QAW039 450 mg once daily QAW039 150 mg once daily Placebo
		5	
		1	
CQAW039A2316 CQAW039A2317	Placebo	3	QAW039 450 mg once daily QAW039 150 mg once daily Placebo
		3	
		1	
CQAW039A2316 CQAW039A2317	150 mg once daily	2	QAW039 450 mg once daily QAW039 150 mg once daily Placebo
		4	
		1	

	Placebo	4 2 1	QAW039 450 mg once daily QAW039 150 mg once daily Placebo
Patients who HAVE NOT PREVIOUSLY PARTICIPATED IN A STUDY OF QAW039: treatment allocation in Study A2315			
Prior study	Treatment group in prior study	Randomization ratio in Study A2315	Treatment group in Study A2315
Not applicable	Not applicable	3 3 1	QAW039 450 mg once daily QAW039 150 mg once daily Placebo

Treatment randomization will be stratified at the regional level.

1.2 Study objectives and endpoints

1.2.1 Primary Objective

Treatment Period 1 (52-week treatment period):

In patients with moderate-to-severe asthma receiving SoC asthma therapy, to evaluate the long-term safety of QAW039 (150 mg once daily and 450 mg once daily), compared with placebo, as assessed by:

- treatment emergent adverse events (AEs);
- treatment emergent serious adverse events (SAEs); and
- study treatment discontinuations due to treatment emergent AEs.

Treatment Period 1 and Treatment Period 2 combined:

In patients with moderate-to-severe-asthma receiving SoC asthma therapy, to evaluate the long-term safety of QAW039 (150 mg once daily and 450 mg once daily), compared with placebo, as assessed by:

- treatment emergent AEs
- treatment emergent SAEs; and
- study treatment discontinuations due to treatment emergent AEs.

1.2.2 Secondary objective(s)

Treatment Period 1 (52-week treatment period):

[figure not shown]
In patients with moderate-to-severe asthma receiving SoC asthma therapy, to evaluate the long-term safety of QAW039 (150 mg once daily and 450 mg once daily), compared with placebo, as assessed by:

- the rate of patients with at least 1 treatment emergent AE by primary system organ class; and
- the rate of treatment emergent patient deaths and patient hospitalizations (any visit to the hospital requiring an overnight stay or an emergency room visit greater than 24 hours) due to an asthma exacerbation.

Treatment Period 1 and Treatment Period 2 combined:

In patients with moderate-to-severe-asthma receiving SoC asthma therapy, to evaluate the long-term safety of QAW039 (150 mg once daily and 450 mg once daily), compared with placebo, as assessed by:

- the rate of patients with at least 1 treatment emergent AE by primary system organ class; and
- the rate of treatment emergent patient deaths and patient hospitalizations (any visit to the hospital requiring an overnight stay or an emergency room visit greater than 24 hours) due to an asthma exacerbation.

2 Statistical methods

2.1 Data analysis general information

2.1.1 General definitions

2.1.1.1 Study treatment

The following investigational treatment will be supplied by Novartis to the study sites:

- Name: QAW039
 - Formulation: tablet
 - Unit dose: 2 strengths: 150 mg and 450 mg
- Name: placebos to QAW039 150 mg and QAW039 450 mg
 - Formulation: tablet

- Unit dose: matching placebo to QAW039 150 mg, matching placebo to QAW039 450mg

The investigational treatment (tablets) will be supplied in bottles. The matching placebos for QAW039 will be identical in appearance to their active counterparts and will be identically packaged. No additional maintenance asthma treatment beyond investigational treatment will be provided for this trial.

Hence for this study the investigational treatment will be referred to as study treatment/drug. The date of the first administration of the investigational treatment (QAW039 or matching placebo) in Study A2315 is referred to as the date of first administration of study treatment in the study.

2.1.1.2 Study day

The first day of administration of randomized study treatment (first dose) is defined as Day 1. All other study days will be labeled relative to Day 1. The day before the first dose of study medication is defined as Day -1.

Therefore, for a particular date, study day will be calculated as follows:

- for dates on or after the first date of study medication,
Study day = Assessment date – Date of first dose of study medication + 1;
- for dates prior to the first date of study medication,
Study day = Assessment date – Date of first dose of study medication.

If a patient never took study medication, the randomization date will be used instead of the date of first dose of study medication. In that case, the randomization date is defined as Day 1 and the day before the randomization is defined as Day -1.

2.1.1.3 Baseline definition

Baseline age will be defined as the age of the patient at study entry in Study A2315 for all patients. Baseline values of other variables are defined as follows for rollover patients and new patients, respectively.

Rollover patients: For laboratory, vital signs, and ECG variables, the last pre-treatment assessment in current study (A2315 baseline) will be used as a primary baseline value for safety monitoring purpose, and prior study baseline (i.e., the baseline value from the previous QAW039 Phase 3 study) will be used as a supplementary baseline value. For other variables, prior study baseline will be used.

New patients: the last pre-treatment assessment in the current study will be used as the baseline value.

Post-baseline measurements are defined as those assessments on or after the start of study treatment in Study A2315.

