3.1 Study design

This study is a 2-treatment period, randomized, multicenter parallel-group safety study (Figure 3-1). Treatment Period 1 is a 52-week, double-blind treatment period in which QAW039 or placebo is added to GINA steps 3, 4 and 5 SoC asthma therapy. Treatment Period 2 is an optional 104-week, single-blind treatment period in which patients will receive QAW039 or placebo added to GINA steps 3, 4 and 5 SoC asthma therapy. **Note:** For the purpose of this study, single-blind will mean investigators and patients will remain blinded while all Novartis personnel will be unblinded.

Eligible patients will include patients completing a prior Phase 3 study of QAW039, as well as patients who have not previously participated in a study of QAW039.

Patients who successfully complete the treatment period of a prior Phase 3 study of QAW039 will be permitted to enter Study A2315 directly upon the completion of the treatment period of the prior study without completing an off drug follow-up period in the prior study. For these patients completing a prior Phase 3 study of QAW039, the last visit of the treatment period in the prior study and Visit 1 of Study 2315 will occur on the same day (i.e., on the last day of study drug treatment in the prior study). Additionally, for patients completing a prior Phase 3 study of QAW039, Visit 201 of Study 2315 will occur the following day (1 day after completion of the last visit of the treatment period of the prior study and Visit 1 of this study [Study A2315]) so there is not any interruption in study drug treatment.

For patients who have not previously participated in a study of QAW039, Visit 1 and Visit 201 of Study 2315 will occur approximately two weeks apart (i.e., Visit 201 should occur approximately two weeks after Visit 1 in Study 2315). This will allow for review of inclusion/exclusion criteria and laboratory values.

For Treatment Period 1 in Study A2315, an informed consent (and assent, if applicable) may be obtained within 14 days prior to or at Visit 1 and before any study-related assessments or procedures are performed. For patients who participated in a prior Phase 3 study, the consent (and assent, if appropriate) for Treatment Period 1 of Study A2315 may be obtained on the last day of the treatment period of the prior Phase 3 study.

For Treatment Period 2, an informed consent (and assent if applicable) will be obtained at Visit 301 for those patients agreeing to participate in this treatment period.

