9.2 Patient demographics and other baseline characteristics

Baseline age will be defined as the age of the patient at study entry in Study A2315. For all other variables in patients completing a prior phase 3 study of QAW039, the baseline value from the prior study will be used as the baseline value for this study (Study A2315). For all variables in patients who have not previously participated in a study of QAW039, the last pre-treatment assessment in the current study (Study A2315) will be used as the baseline value.

Patient demographics and baseline characteristics including age, sex, race, ethnicity, height, weight, body mass index (BMI), relevant medical history, smoking history, asthma duration, background therapies, pre- and post-bronchodilator FEV1, percent predicted FEV1, [REDACTED], number of exacerbations in the previous year prior to screening will be summarized by treatment group for the FAS. Categorizations of age will include at least the categories of <18 years of age and ≥ 18 years of age.

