2.8.3 Laboratory data

Laboratory data consist of hematology, biochemistry and urinalysis. On-treatment laboratory data will be summarized. Laboratory data measured on or after first intake of study drug and until 7 days after last intake of study drug are regarded as on-treatment data. All data will be included in the analyses regardless of rescue medication use. The following sub-sections will describe the method of summary. For rollover patients, the last pre-treatment assessment in the current study (A2315 baseline) will be used in summary tables and figures. Prior study baseline will be considered as a supplementary baseline value presented in figures as well.

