Sodium (mmol/L)	125	160
Gamma GT (U/L)		3 x ULN
CPK (IU/L)		4 x ULN
Urinalysis		
Dipstick blood		≥ 2+
Dipstick glucose		≥ 2+
Dipstick leukocytes		≥ 2+
Dipstick protein		≥ 2+
v = volume, ULN = upper limit of normal		

Liver function tests

To evaluate potential drug-induced liver injury, newly occurring or worsening abnormalities in liver function tests will be evaluated (see Table 2-4 for a summary of the notable values).

When a criterion contains multiple laboratory parameters, the criterion will only be considered to be met when all conditions occur at the same time (i.e., in the same sample). A case where all criteria are met at a post-baseline time point but not met at baseline will be considered as newly occurring. A case will be considered as worsening if all the criteria are met at baseline and at least one component is worsening from baseline, irrespective of whether the other(s) are better.

The number and percentage of patients with newly occurring liver enzyme abnormalities any time post-baseline will be summarized by source of patients. Listings of patients with notable liver function test lab values and liver events will be provided.

To evaluate drug induced serious hepatotoxicity eDish plots will be presented by source of patients and treatment in prior study for rollover for rollover patients. The eDish plot will reflect the worst value of each of the parameters; they do not need to occur at the same visit.

Table 2-4 Notable liver function test values

Criterion
ALT > 3 x ULN ALT > 5 x ULN ALT > 8 x ULN ALT > 10 x ULN ALT > 20 x ULN
ALT or AST > 3 x ULN ALT or AST > 5 x ULN ALT or AST > 8 x ULN ALT or AST > 10 x ULN ALT or AST > 20 x ULN
Total Bilirubin > 1 x ULN Total Bilirubin > 1.5 x ULN Total Bilirubin > 2 x ULN Total Bilirubin > 3 x ULN
ALP > 1.5 x ULN ALP > 2 x ULN ALP > 3 x ULN ALP > 5 x ULN
ALT or AST > 3 x ULN and Total Bilirubin > 1.5 x ULN ALT or AST > 3 x ULN and Total Bilirubin > 2 x ULN ALT or AST > 5 x ULN and Total Bilirubin > 2 x ULN ALT or AST > 8 x ULN and Total Bilirubin > 2 x ULN ALT or AST > 10 x ULN and Total Bilirubin > 2 x ULN ALT or AST > 20 x ULN and Total Bilirubin > 2 x ULN
ALP > 3 x ULN and Total Bilirubin > 2 x ULN ALP > 5 x ULN and Total Bilirubin > 2 x ULN
ALT or AST > 3 x ULN and Total Bilirubin > 2 x ULN and ALP ≤ 2 x ULN (Hy's law)
ALT or AST > 3 x ULN and (nausea or vomiting or fatigue or general malaise or abdominal pain or (rash and eosinophilia))*

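### For rollover patients already treated with QAW039, the SAP's lab, ECG and vital-sign tables use an on-drug baseline, so a stable abnormality acquired in the prior study is not counted as new or as change

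*SAP*

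**What the plan says.** Protocol 9.2 sets one rule for rollover patients. Age is taken at entry to A2315; for every other variable "the baseline value from the prior study will be used as the baseline value for this study".

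SAP 2.1.1.3 changes this for laboratory, vital-sign and ECG variables: "the last pre-treatment assessment in current study (A2315 baseline) will be used as a primary baseline value for safety monitoring purpose". The same sentence keeps the prior-study value, which "will be used as a supplementary baseline value".

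SAP 2.8.3 then allocates the two baselines to outputs. For rollovers, "the last pre-treatment assessment in the current study (A2315 baseline) will be used in summary tables and figures", whereas "Prior study baseline will be considered as a supplementary baseline value presented in figures as well". SAP 2.8.4.1 (ECG) and 2.8.4.2 (vital signs) say the same. No table is specified against the prior-study baseline.

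Protocol 3.1 places Visit 1 on the last day of prior-study treatment and Visit 201 on the next day, "so there is not any interruption in study drug treatment".

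**The concern.** The A2315 value is drug-free for new patients and for rollovers who took placebo before. For rollovers who took QAW039 before, it is measured under treatment. If the drug raised a liver enzyme or lengthened QTcF during the prior study, that effect is already in the reference value.

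These patients were enrolled to lengthen exposure to QAW039, so they are the ones in whom slow or cumulative effects would show. With two baselines, one continuous exposure is cut in two, and each report shows only its own part. Other parts of the plan do not close the gap:

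- Protocol 9 leaves analyses that combine the prior studies to separate, optional pooled work outside this study report.
- SAP 2.3 treats adverse events still ongoing from the prior study as medical history, so they do not enter the A2315 treatment-emergent tables.
- The laboratory exclusion at Visit 1 (criterion 19b) applies to new patients only, so a rollover can enter with an abnormal value.

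**Working it through.** **Step 1. The plan's own allocation figures.** From Protocol Table 5-1, the smallest chance of keeping the prior QAW039 dose is min(5/7, 5/7, 4/7) = 57.1%; the plan states at least 57%. The chance of active treatment is 6/7 = 85.7%; the plan states approximately 85%. Both reproduce.

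**Step 2. How many patients have an on-drug baseline.** Inputs: Table 5-1 ratios, and 1,000 rollovers plus 570 new patients (Protocol 9.8). Two things are not given and are assumed: equal arm sizes within each prior study, and the share f of rollovers coming from A2307/A2314, taken over its whole range 0 to 1. Equal prior arms fit the planned overall 3:3:1, since (5+1+3)/3 = 3 and (2+4)/2 = 3 for each dose, but the documents do not state them.

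| A2315 arm | Prior QAW039, rollovers from A2307/A2314 | Prior QAW039, rollovers from A2316/A2317 | Range over f |
|---|---|---|---|
| 450 mg | (5+1)/(5+1+3) = 67% | 2/(2+4) = 33% | 33–67% |
| 150 mg | (1+5)/(1+5+3) = 67% | 4/(4+2) = 67% | 67% |
| Placebo | 2/3 = 67% | 1/2 = 50% | 50–67% |

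- All rollovers: 1,000 × (1/2 to 2/3) = 500 to 667. Over 1,570 that is 32% to 42%. The other 333 to 500 rollovers have a drug-free baseline.
- Whole dose arm: 1,570 × 3/7 = 673. For 150 mg, 1,000 × 3/7 × 2/3 = 286, or 42%. For 450 mg, 143 to 286, or 21% to 42%.
- Whole placebo arm: 1,570/7 = 224. Prior QAW039 in 71 to 95, or 32% to 42%.

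**Step 3. What the counting rules do.** Under SAP 2.8.3.3, a newly occurring notable value needs a non-notable baseline, and a worsening one needs a notable baseline and a worse later value. The liver table counts "The number and percentage of patients with newly occurring liver enzyme abnormalities any time post-baseline".

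*ALT, assumed values, ULN 40 (3×ULN = 120, 5×ULN = 200).* Prior-study baseline 30; A2315 baseline 130.

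| Later value | Against A2315 baseline | Against prior-study baseline |
|---|---|---|
| 130 | change 0; not new, not worsening | change +100; new above 3×ULN |
| 135 | change +5; worsening, not new | change +105; new above 3×ULN |
| 210 | change +80; worsening, and new above 5×ULN | change +180; new above 3× and 5×ULN |

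Only the unchanged value (or one that falls) escapes both counts. The value of 135 enters the notable-value table as worsening but not the liver table of new cases.

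*QTcF, assumed values.* A rise of 20 msec in the prior study and another 20 msec in A2315 gives +20 in this study's table, below the 30 msec category in SAP 2.8.4.1. Against the prior-study baseline it is +40, inside the category. The prior study on its own would also have shown only +20.

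**Step 4. Is the change declared?** The legible items in SAP Section 4 do not list a change of baseline. Some items there are redacted, so the documents do not show whether it was recorded.

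**The case against.** The strongest case for the SAP is the design. Patients are re-randomised at Visit 201 within strata of prior treatment, and the study report rests on A2315 data alone. The A2315 value is measured before randomisation, is available for new and rollover patients alike, and is the right reference for effects that begin in this study. An abnormality that arose in A2307 or A2316 belongs to that study. This stands: the randomised comparison is not biased by the SAP's choice, and the A2315 baseline should remain.

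It is also fair that other outputs show some carried-over effects:

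- absolute and worst-case laboratory values, and worsening counts;
- persistent or recurrent ECG abnormalities;
- eDish plots of worst values, already split by treatment in the prior study;
- creatinine change, which is planned as plots, the format in which the prior-study baseline is shown.

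Entry rules reduce the problem further. Rollovers must have completed prior treatment without a serious drug-related event and be judged able to continue safely. Protocol 5.6.2 lists QTcF at or above 450 msec (male) or 460 msec (female) at Visit 201 among its reasons to discontinue study treatment, which limits the issue for QTcF thresholds. It remains for QTcF increases and for laboratory values.

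A reader might go further and infer that the SAP dilutes a drug-to-placebo ratio by a calculable factor, which the prior-study baseline would restore. The documents do not support that, because half to two thirds of placebo rollovers also had prior QAW039. Suppose, purely for illustration, that QAW039 causes a persistent abnormality in 3% against a background of 1%, and that it outlasts a switch to placebo. On the prior-study baseline, rollovers now on placebo would show 2/3 × 3 + 1/3 × 1 = 2.3% (A2307/A2314) or 1/2 × 3 + 1/2 × 1 = 2.0% (A2316/A2317). The pooled ratio would be 3/2.3 = 1.3 or 3/2.0 = 1.5, and 1.0 among those with prior QAW039. A pooled comparison with placebo on that baseline would be contaminated.

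**Conclusion.** The point holds in limited form. For rollovers previously on QAW039, the tables cannot count a stable abnormality acquired in the prior study as new or as change, and they split cumulative shifts. Protocol 9.2 specified the baseline that would show both. Under the equal-arms assumption this concerns 500 to 667 patients: two thirds of rollovers on 150 mg, one third to two thirds on 450 mg, and half to two thirds on placebo. How many of them carry such an abnormality cannot be estimated from the documents.

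Three wider readings are not supported:

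- It does not apply to rollovers as a whole, since those from prior placebo have a drug-free baseline.
- Affected patients are a sure majority of rollovers only in the 150 mg arm.
- The abnormalities are not invisible, because the figures and the baseline-free outputs can show them.

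What is missing is a tabulated count of change since first exposure in the longest-exposed patients.

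**What to change.** Keep the A2315 baseline as primary for the randomised comparison. For rollover patients, add a second set of three table groups against the prior-study baseline:

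- notable values;
- newly occurring liver abnormalities;
- new or increased QTcF.

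Split each by prior treatment as well as by A2315 arm. Label them descriptive, as change since first exposure, and draw no pooled comparison with placebo from them. In SAP Section 4, state the departure from Protocol 9.2 and the reason for it, unless a redacted item already does.

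The cost is a second run of existing table programs and more output to review. The prior-study baseline is already needed for the figures, so no new data are required.

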2.1.1.4 Change from baseline

When change from baseline is of interest the following formula will be used for each scheduled visit and time-point where baseline and post-baseline values are both available:

Change from baseline = post-baseline value – baseline value; and

If baseline or post-baseline values are missing, then the change from baseline will be missing.

